11.5.1 Secondary objectives

To assess all-cause mortality in the aCRT ON arm compared to aCRT OFF.

Mortality will be illustrated with Kaplan-Meier graphs. A Cox proportional hazards regression model will be used to estimate the HR of aCRT compared to control, which will be reported with its p-value and 95% confidence interval. The model will include the stratification variables also included in the primary objective model.

To assess the rate of intervention for heart failure decompensation for aCRT ON compared to aCRT OFF.

Incidence of intervention for heart failure decompensation will be illustrated with cumulative incidence graphs. A Cox regression model will be used to estimate the cause-specific HR of aCRT compared to control, which will be reported with its p-value and 95% confidence interval. The model will include the stratification variables also included in the primary objective model. Additionally, recurrent event survival analysis will be performed to compare rates of interventions for heart failure decompensation.

To test the hypothesis that aCRT ON increases the proportion of patients that improve on the Clinical Composite Score (CCS) compared to aCRT OFF, at 6 months of follow-up.

The Clinical Composite Score classifies patients according their clinical status at 6 months post randomization into categories Improved, Unchanged, and Worsened²². A patient is classified Worsened in case of death, hospitalization for worsening heart failure, worsened NYHA class (using last observation carried forward), or worsened status on the Global Assessment Score. Also patients that exit the study or cross over because of worsening heart failure are classified Worsened. A patient is classified Improved when not Worsened and there is an improvement in NYHA class or Global Assessment Score. Patients that are not Worsened or Improved are Unchanged.

The proportion of patients who Improved will be compared between the arms of the study with a logistic regression model, correcting for the stratification variables also included in the primary objective model.

To test the hypothesis that aCRT reduces the incidence of AF compared to aCRT OFF.

Incidence of AF will be determined from device data, and the endpoint for the primary analysis will be the first day after randomization on which there is >6 hrs of AF reported in the device's Cardiac Compass Trends. The analysis will compare incidence of AF using survival analysis methods. As secondary analyses device measured AF burden and treatment for AF will be analyzed.

To test the hypothesis that the change in quality of life, measured by the KCCQ, in the aCRT ON group is better than the change in the aCRT OFF group.

The parameter of interest is the KCCQ overall summary score (range, 0 to 100; higher scores indicate better health status) which will be assessed at baseline and at the 3, 6, 12, 18, and 24 months follow-up visits. The summary score at the follow-up visits will be analyzed using a linear mixed effects regression model that will account for the correlation of scores within each patient. The treatment arm allocation will be included as a main effect. The baseline KCCQ score as well as the stratification variables included in the primary objective model will be included as covariates in the model. Analysis will be corrected for time trends if needed.

To test the hypothesis that the change in health outcome, measured by the EQ-5D, in the aCRT ON group is better than the change in the aCRT OFF group.

The parameter of interest is the EQ-5D index, which will be assessed at baseline and at the 3, 6, 12, 18, and 24 months follow-up visits. Derivation of the index will follow instructions provided by the EuroQol Group (www.euroqol.org). The index at the follow-up visits will be analyzed using a linear mixed effects regression model that will account for the correlation of measurements within each patient. The treatment arm allocation will be included as a main effect. The baseline EQ-5D index as well as the stratification variables included in the primary objective model will be included as covariates in the model. Analysis will be corrected for time trends if needed.

To test the hypothesis that aCRT reduces the incidence of all-cause re-admissions after a heart failure (HF) admission within 30-days of the index event.

A negative binomial model will be used to estimate and compare incidence rates of all-cause re-admissions after an HF admission. For each patient the number of hospital admissions that falls within 30 days of discharge from an HF admission (as classified by the investigator) will be determined. All patients will be included in the model, with a count of zero in case no 30-day readmissions occurred. The model will include an offset based on the total follow-up experience of all patients.

To assess cost-effectiveness of CRT devices with the aCRT algorithm relative to traditional CRT devices.

Analysis method for this objective will be defined in the Economic Analysis Plan. There will be no hypothesis test and therefore the objective will not be included in the Hommel multiple testing procedure.

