5.6 Blinding

The study will be single-blinded (i.e. subjects are blinded to randomization assignment) to reduce the effect of bias. Every effort must be made to ensure the randomization assignment is not revealed to the subject.

The Data Monitoring Committee (DMC) will regularly review summarized adverse event data to address potential safety issues. The DMC will be unblinded to subject treatment assignments. However; the EAC will be blinded to the treatment designation when reviewing case files, wherever reasonably achievable.

After all study tests and procedures have been completed just prior to subject exit from the study, the subject may be informed (verbally or in written form) of their randomization assignment.

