6.8 Randomization

Subjects will be assigned to a treatment at random during the randomization visit, which must occur within 7 days after a successful implant. Centers will receive this assignment electronically in the study database from Medtronic upon completion of the randomization case report form.

At the time of the randomization device programming, a device check will be conducted and the default settings will be verified. If subjects are assigned to the aCRT ON group, "Adaptive Bi-V and LV" will be programmed. If subjects are assigned to the aCRT OFF group, the delegated person will ensure that "Nonadaptive CRT" is programmed. Control group subjects will be optimized per physician's discretion. The method of AV and VV optimization in the control group will be collected. Full device interrogation (Interrogate ALL) data will be collected reflecting the final programming, and a copy of the interrogation files must be sent to Medtronic with a copy being maintained at the center in the subject's file.

The following procedures will be completed / data will be collected at the randomization visit:

- Device programming according to assignment
- AV/VV optimization method (control group only, if optimization occurs per standard of care)
- Final device interrogation (Interrogate All)
- Report AEs, System Modifications, Study Deviations, Crossovers, and Healthcare Utilizations (as they occur)

If randomization does not occur within 37 days after enrollment, verification of all inclusion and all exclusion criteria must be repeated before randomization.

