The EAC will review all applicable Healthcare Utilizations and all study reportable events during the study, assessing outpatient treatment and hospitalizations, to determine HF relatedness and AF relatedness for the study objectives.

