4.4.7 Secondary Objective #7: All-cause re-admission after an heart failure admission within 30 days of the index event

The secondary objective #7 is to test the hypothesis that aCRT reduces the incidence of all-cause re-admissions after a heart failure (HF) admission within 30 days of the index event.

Hypothesis

Assuming the number of all-cause re-admissions after a HF admission within 30 days of the index event follows a Negative Binomial distribution, $P_T(Y=k)$ and $P_C(Y=k)$ denote the expected probability of having k all-cause re-admissions after a HF admission within 30 days of the index event, for $k=0, 1, 2, \dots$, in the aCRT ON arm and aCRT OFF arm, respectively. The rate ratio (RR) for aCRT treatment is the ratio of the number of all-cause re-admissions after a HF admission within 30 days of the index event per patient year, in the aCRT ON arm relative to that in the aCRT OFF arm. The corresponding null and alternative hypotheses are:

$$H_0 : RR = 1$$

$$H_A : RR \neq 1$$

Endpoint Definition

For this secondary objective, an index event must satisfy the following conditions:

- It is a heart failure admission;
- It is not within 30 days of the discharge from a previous index event;

Analysis Method

The analysis unit is patient. A subject could have multiple HF admissions that are index events. The total number of 30-day all-cause readmissions is aggregated over all index events and summarized into a single count per patient. The 30-day all-cause re-admission rate after an index HF hospitalization will be compared between aCRT ON and aCRT OFF arm using a Negative Binomial model with random site effect and NYHA at enrollment as a covariate. An offset based on the total follow-up experience of all patients will be included. If the last heart failure admission occurred after 30 days of the discharge from the previous index event, however, the patient died or exited within the 30 days after the last heart failure admission, the total follow-up time will count up to one day before the last heart failure admission. The SAS code will be similar to:

```
proc glimmix data=HFIndexReadmit;
class site rand NYHA;
model nReAdmit30Days = rand NYHA / dist=negbin link=log
                                offset=ln_followyrs;
random intercept / subject=site;
run;
```

Missing Data

Since the endpoint of this objective is a variable for counts starting from 0, missing data is not expected.

[REDACTED]

[REDACTED]

[REDACTED]

[REDACTED]

[REDACTED]

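### The 30-day readmission endpoint takes its index heart failure label from unblinded investigators, although the blinded adjudication committee already decides HF relatedness

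*Protocol*

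**What the plan says.** The readmission objective is in Protocol 11.5.1. For each patient, the admissions in the 30 days after leaving hospital from an HF admission are counted, with the HF admission taken "as classified by the investigator", and the counts are compared between arms with a negative binomial model. The objective is one of the secondary hypotheses under the Hommel procedure (Protocol 11.5, SAP 4.4).

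On blinding, Protocol 5.6 states: "The study will be single-blinded (i.e. subjects are blinded to randomization assignment) to reduce the effect of bias". Investigators are not listed as blinded. Protocol 6.8 adds: "Centers will receive this assignment electronically in the study database from Medtronic upon completion of the randomization case report form". The center then programs the device to the assigned mode.

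On adjudication, Protocol 8.2.2 has the EAC review healthcare utilizations and reportable events, "assessing outpatient treatment and hospitalizations, to determine HF relatedness and AF relatedness for the study objectives". Appendix D says that the committee decides which events count toward the primary and secondary endpoints.

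The endpoint definition in SAP 4.4.7 sets two conditions for an index event. The first is "It is a heart failure admission"; the second is that it does not fall within 30 days of discharge from a previous index event. No classifier is named. SAP Table 2 lists only a primary analysis for secondary objectives #3 to #7.

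**The concern.** A readmission enters the count only if the admission before it was labelled HF. The label is a clinical judgement, and Protocol 11.5.1 gives it to someone who can know the arm. If labelling depends on the arm, even without intent, the count in one arm shifts and the rate ratio shifts with it. The shift could create an apparent benefit or hide a real one.

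The Hommel procedure controls error across several tests. It gives no protection when the outcome itself is ascertained differently by arm. A result on this endpoint would still be reported as significant under strict family-wise control.

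The plan gives its own reason for avoiding this. Protocol 11.2.1 relies on independent blinded adjudication for an unbiased comparison of the arms, and Protocol 5.7 lists it among the bias controls. For this endpoint the plan forgoes that control and gives no reason.

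**Working it through.** **Comparison of the texts.** The plan states no expected count, rate, effect size or power for this endpoint, so there is no figure to reproduce. The check is mainly one of text.

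1. *Who labels the index admission?* The investigator (Protocol 11.5.1).
2. *Can the investigator know the arm?* Yes. Only subjects are blinded (5.6), and the center receives the assignment and programs the device (6.8).
3. *Does a blinded label exist?* Yes. All hospitalizations are reportable healthcare utilizations, and this information feeds the EAC's review of potential HF events (6.12). The EAC determines HF relatedness (8.2.2) and which events count for secondary endpoints (Appendix D).
4. *Do the documents agree?* No. Section 11.5.1 names the investigator, while 8.2.2 and Appendix D name the EAC.
5. *Does the SAP settle it?* Not in its visible text. The endpoint definition in 4.4.7 names no classifier, and Table 2 plans no sensitivity analysis for this objective.
6. *Is the endpoint tested?* Yes. Eight secondary objectives less cost-effectiveness leaves seven in the Hommel family.

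**How a label difference reaches the estimate.** In each arm the expected count is approximately follow-up time × rate of true HF admissions × probability of an HF label × mean 30-day readmissions per index admission. The model's offset is follow-up time, not the number of HF admissions, so a lost label lowers the numerator and barely changes the denominator. If the arms differ only in labelling, with relative frequency r (aCRT ON / aCRT OFF), the observed rate ratio is about r.

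**Illustrative size.** Assumptions, none of them in the documents: true rate ratio 1; D = 100 to 400 counted readmissions in total; overdispersion φ = 1.0 to 1.5. Then

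- D_C = D/(1 + r) and D_T = D − D_C
- SE = √[φ(1/D_T + 1/D_C)] and m = ln(r)/SE
- two-sided false-positive rate = Φ(−z − m) + Φ(−z + m)

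Example with r = 0.90, D = 200, φ = 1.0: D_C = 105.3 and D_T = 94.7; SE = 0.1416; m = −0.1054/0.1416 = −0.744. At α = 0.05 the rate is Φ(−1.216) + Φ(−2.704) = 0.112 + 0.003 = 11.5%.

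| r | α = 0.05 | α = 0.05/7 = 0.0071 |
|---|---|---|
| 1.00 | 5.0% | 0.71% |
| 0.95 | 5.5–8.1% | 0.8–1.5% |
| 0.90 | 7.1–18.3% | 1.3–5.1% |
| 0.80 | 14.8–60.2% | 3.7–31.8% |

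The lower end of each range is D = 100 with φ = 1.5; the upper end is D = 400 with φ = 1.0. The second column uses the final-stage α of 0.05 for a single test. The third is the Bonferroni floor for seven hypotheses. With r below 1 the excess favours aCRT ON; with r above 1 it would favour control.

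**The case against.** The best counter-argument is that the exposure is narrow and its size unknown.

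- **Only the index label needs judgement.** The readmission counted is all-cause. This stands, but the label decides whether the readmission is counted at all.
- **The 5–10% figure and its direction are assumed.** This stands. Proportionality also needs relabelled admissions to carry the same readmission risk as the rest, which borderline cases may not. In addition, when an admission loses its HF label, a later HF admission within the 30 days may become an index event and offset part of the loss.
- **The committee label is not perfectly blind.** Protocol 5.6 qualifies EAC blinding by what is practicable, and the committee works from material supplied by unblinded sites. Decisions to admit or readmit also stay with unblinded clinicians. Adjudication therefore reduces the risk and may not remove it, but it is still better than a label set with knowledge of the arm.
- **The SAP may contain a further rule.** Text after the missing-data paragraph of 4.4.7 is redacted, so this cannot be excluded. The endpoint definition itself is visible, however, and names no classifier.
- **The EAC may not label every admission.** Protocol 8.2.2 limits its review of healthcare utilizations to applicable ones. The same sentence also covers all reportable events, which under 8.1.1 include all serious and all cardiovascular events. HF admissions would fall within that.
- **Other sections already point to the EAC.** True, and this makes 11.5.1 an internal conflict as well as a weaker choice. That adds to the reason for changing it.

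**Conclusion.** The concern holds. Protocol 11.5.1 takes an unblinded label for a formally tested secondary endpoint where a blinded one is already planned, and it conflicts with Protocol 8.2.2 and Appendix D. The visible SAP text does not resolve the conflict.

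Confidence is high that the route for bias exists. Its size and direction cannot be established from the documents, and the illustrative false-positive rates depend entirely on the assumed r, D and φ. At r = 0.95 the inflation is modest; at r = 0.90 it can be more than threefold (18.3% against 5.0%). The primary endpoint is not affected, because the EAC adjudicates it.

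**What to change.** In Protocol 11.5.1 and SAP 4.4.7, define the index event as a hospital admission that the EAC adjudicated as HF-related. Restricting it to hospital admissions matters because the committee's HF events also include outpatient IV treatment (Protocol 11.2.1). Keep the rule on successive index events as it is.

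Add the analysis based on the investigator label as a sensitivity analysis in SAP 4.4.7 and Table 2, and report how often the two labels agree in each arm. Make the change before the lead statistician is unblinded.

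The cost is about one sentence in each document plus the table entry. No new data should be needed, since the adjudications are already planned; confirm that every HF admission, including those after a patient's first event, receives an EAC label.

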11.5.2 Ancillary objectives

Analysis methods for ancillary objectives will be defined in the Statistical Analysis Plan.

12. DATA AND QUALITY MANAGEMENT

Data will be collected using an electronic data management system for clinical studies. Case Report Form (CRF) data will be stored in a secure, password-protected database which will be backed up nightly. Data will be reviewed using programmed and manual data checks. Data queries will be made available to centers for resolution. Study management reports may be generated to monitor data quality and study progress. At the end of the study, the data will be frozen and will be retained by Medtronic.

The data reported on the CRFs shall be derived from source documents and be consistent with these source documents, and any discrepancies shall be explained in writing. Source documents, such as patient charts, ECGs, device interrogation files, worksheets, and lab results, must be created and maintained by the investigational site team. For source documentation, the investigational center study team must sign and date any copies or printouts of original source documents with a statement that this is complete and true reproduction of the original source document.

Device data from CareLink transmissions will be uploaded to secure servers and made accessible to the study team. Device interrogation files collected via electronic media at office visits will be sent to Medtronic. Upon receipt via transmission or electronic media, device data will be maintained within secure databases and retrieved for analysis and reporting.

The sponsor or a regulatory authority may audit or inspect the study center to evaluate the conduct of the study. The clinical investigator(s)/institution(s) shall allow study related monitoring, audits, Ethics Committee review, and regulatory inspection(s) by providing direct access to source data/documents. If study site's documents are electronic, these must be made available in their original form (or print outs signed and dated with the statement that this is complete and true reproduction of the original source document) if requested by the sponsor and/or regulatory authority. Study sites should inform Medtronic upon notification of an audit by a regulatory body immediately.

13. WARRANTY/INSURANCE INFORMATION

13.1 Warranty

Warranty information is provided in the product packaging for the commercially released CRT devices and leads, and additional copies are available upon request.

13.2 Insurance (Europe, Russia and Middle East)

Medtronic Bakken Research Center B.V. is a wholly owned subsidiary of Medtronic, Inc., which as the parent company of such entity maintains appropriate clinical study liability insurance coverage as required under applicable laws and regulations and will comply with applicable local law and custom concerning specific insurance coverage. If required, a Clinical Trial insurance statement/certificate will be provided to the Ethics Committee.

13.3 Insurance (Japan)

Information regarding warranty and compensation will be provided under separate cover per the local regulation. Documentation explaining compensation to the subjects in the event of study-related injuries will be submitted to Ethics Board if required.

13.4 Insurance (Australia)

Medtronic Australasia Pty Ltd is a wholly owned subsidiary of Medtronic, Inc., which as the parent company of such entity maintains appropriate clinical study liability insurance coverage as required under applicable laws and regulations and will comply with applicable local law and custom concerning specific insurance coverage. If required, a Clinical Study insurance statement/certificate will be provided to the Ethics Committee.

13.5 Insurance (India)

India Medtronic Pvt. Ltd. is a wholly owned subsidiary of Medtronic, Inc., which as the parent company of such entity maintains appropriate clinical study liability insurance coverage as required under applicable laws and regulations and will comply with applicable local law and custom concerning specific insurance coverage. If required, a Clinical Study insurance statement/certificate will be provided to the Ethics Committee.

13.6 Insurance (Korea)

Medtronic Korea Co., Ltd. is a wholly owned subsidiary of Medtronic, Inc., which as the parent company of such entity maintains appropriate clinical trial liability insurance coverage as required under applicable laws and regulations and will comply with applicable local law and custom concerning specific insurance coverage. If required, a Clinical Trial insurance statement/certificate will be provided to the Ethics Board.

13.7 Insurance (Taiwan)

Medtronic Taiwan Ltd. is a wholly owned subsidiary of Medtronic, Inc., which as the parent company of such entity maintains appropriate clinical trial liability insurance coverage as required under applicable laws and regulations and will comply with applicable local law and custom concerning specific insurance coverage. If required, a Clinical Trial insurance statement/certificate will be provided to the Ethics Board.

13.8 Insurance (Latin America)

Medtronic USA Inc. is a wholly owned subsidiary of Medtronic, Inc., which as the parent company of such entity maintains appropriate clinical trial liability insurance coverage as required under applicable laws and regulations and will comply with applicable local law and custom concerning specific insurance coverage. If required, a Clinical Trial insurance statement/certificate will be provided to the Ethics Board.

